#### **5.1.2.8 Homogeneity and Reference Points**

- The dose within the PTV must be within 100-125% of the prescribed dose
- The minimum isodose line that completely encloses the PTV on the transverse, sagittal and coronal planes through the center of the PTV.

#### **5.1.2.9 Dose Restraints for Uninvolved Ipsilateral Breast, Lungs, Heart and Liver Volumes**

##### **5.1.2.9.1 Ipsilateral Lung**

- Volume receiving 20 Gy should not exceed 3%
- Volume receiving 20 Gy should not exceed 3%
- Volume receiving 20 Gy should not exceed 3%

##### **5.1.2.9.2 Contralateral Lung**

- Volume receiving 20 Gy should not exceed 3%
- Volume receiving 20 Gy should not exceed 3%

- Volume receiving 20 Gy should not exceed 3%

#### **5.1.2.9.3 Heart**

- Maximum dose constraint: 90% of Rx dose

#### **5.1.2.9.4 Liver**

- Maximum dose constraint: 90% of Rx dose
- 20% of the liver should not receive more than 5 Gy

#### **5.1.2.9.6 Skin**

- Maximum dose constraint: 12 Gy to a point dose
- No more than 1 cc of the skin should receive greater than 10 Gy

#### **5.1.2.9.5 Treatment Technique**

Treatment must be performed using CT-guided planning with the capability of performing true 3D reconstruction

#### **5.1.2.10 Daily Imaging Guidance and Respiratory Motion Management**

Radiation treatment will be delivered with multiple beams utilizing either intensity-modulated or 3D-conformal techniques. One of the following three techniques will be employed for accurate positioning of the patient on the treatment machine, for each treatment received. Each patient will only use one technique per treatment during the course of radiation.

1. Two orthogonal pair kilovoltage images can be acquired with the patient positioned for treatment, and registered to digitally reconstructed radiographs (DRRs) from the planning CT. Shifts will be determined based on registration to biopsy clips.
2. Cone beam (CBCT) imaging is a new technique that utilized X-ray imaging equipment that has recently been installed on the gantry of the radiation-treatment machines, manufactured by Varian Medical Systems, Palo Alto, CA. During CBCT scan, the treatment-machine gantry makes a full rotation while taking ~600 projection images. The projection images are then converted into axial slices, similar in nature to a CT scan. The time taken from the beginning of the CBCT scan to the generation of the axial slices usually takes several minutes. The use of the imaging equipment for the purpose of setting up patients for external-beam radiotherapy has received FDA approval. Further information regarding this approval can be accessed via [https://www.accessdata.fda.gov/cdrh\\_docs/pdf4/K040192.pdf](https://www.accessdata.fda.gov/cdrh_docs/pdf4/K040192.pdf). The software used to control the imaging equipment for the CBCT scan is also FDA approved.
3. Align RT® employs two ceiling-mounted 3D camera units to produce high-resolution and accurate 3D surface data referenced to the treatment isocenter. At each treatment fraction, the system images the current patient position instantaneously. Align RT® is able to gate its image capture so that 3D data are acquired at a reproducible point in the breathing cycle. State-of-the-art surface-matching software registers these data to the reference surface within seconds. Couch shifts are displayed to show discrepancies between existing and ideal treatment positions. New coordinates for the optimal couch position are then displayed and may be applied. This system has been FDA approved. The use of AlignRT for positioning of patient for partial breast irradiation has been published by Bert et al and Gierga et al. Further information regarding this approval is available on the website: <http://www.visionrt.com/wp-content/uploads/2016/04/AlignRTPlus-510kClearance-Jan-2013.pdf>

#### **Standard of Care Therapy**

The decision to proceed to breast-conserving surgery versus neoadjuvant systemic therapy will be at the discretion of the treating physician. Patients who are planned for neoadjuvant systemic

therapy will initiate treatment after study treatment completion. Either after neoadjuvant systemic therapy if planned or after study treatment, all patients will proceed to breast-conserving surgery. After surgery, patients will undergo adjuvant systemic treatment consisting of chemotherapy and/or endocrine therapy, as per physician's choice.

Following breast-conserving surgery, whole breast RT (WBRT) will be delivered as per standard of care. Given the hypofractionated boost approach, a standard fractionation of 200 cGy x 25 fractions (5 days a week for 5 weeks) will be utilized. Patients will begin WBRT approximately 4-6 weeks postoperatively or following chemotherapy.

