## STUDY SCHEMA

This is a prospective, phase Ib/II study of the preoperative combination of pembrolizumab (pembro) and radiation therapy (RT) in patients with operable breast cancer. Patients with newly diagnosed, Stage I-III breast cancer who are planned for breast-conserving surgery and adjuvant whole breast radiation therapy will be recruited into one of 2 cohorts as per their biomarker profile as depicted below. The TNBC cohort will have 50 subjects (10 TNBC subjects for phase Ib and 40 TNBC subjects for phase II) and the HR+ cohort will have 10 subjects. Enrollment will start with the phase Ib TNBC cohort. The trial will be conducted in a Bayesian design, wherein safety as assessed by lack of delay in standard of care treatment will be assessed after 3, 6, and 9 patients have initiated standard of care treatment in each cohort. Standard of care treatment is defined as breast-conserving surgery or initiation of neoadjuvant systemic chemotherapy. If the phase Ib TNBC trial meets a pre-specified safety endpoint, enrollment in

the phase II TNBC trial and HR+ cohort will take place.

Study treatment will consist of 2 doses of neoadjuvant pembro. The second dose will be given in combination with a RT boost. The primary objectives are: 1) to assess the feasibility of the preoperative combination of pembro and RT as defined by the number of patients who do not necessitate a delay in standard of care treatment, 2) to assess the change in tumor infiltrating lymphocyte (TIL) score with therapy. The secondary objectives are to describe the toxicity with preoperative pembro and RT up to 15 weeks after administration of pembrolizumab, to assess the invasive disease-free (iDFS) survival, and to assess the pathological complete response (pCR) rates.

- The first dose of pembro will be given on cycle 1, day 1 (C1D1). Each cycle will be 21 days. The second of pembro dose will be given on C2D1 (+/- 3 days).
- RT will be administered concurrently within one week of the second dose of pembro (C2D1 + 5 calendar days). 8Gy will be delivered in 3 fractions over 3 to 5 business days (for a total dose of 24Gy).
- Standard of care treatment, including breast-conserving surgery or additional neoadjuvant systemic therapy, will be pre-set to start 8 weeks after study enrollment (+/- 5 days).
- Research blood and stool will be obtained after consent up to C1D1. It will also be obtained on C2D1 (+/- 3 days) and at the time of initiation of standard of care treatment (+/- 5 days).

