#### **1.3.2 Clinical Data**

A systemic response to localized RT in combination with anti-CTLA-4 therapy, the so-called “abscopal effect”, was reported in a patient after disease progression with CTLA-4 blockade with ipilimumab alone. Specifically, a right hilar lymph node and spleen metastases, which was not the target of RT, showed regression only after the patient received palliative RT after several months of anti-CTLA-4.

Based on the above phenomenon as well as pre-clinical data suggesting the synergism of RT with immune therapies, studies evaluating the efficacy of RT with checkpoint blockade in metastatic breast cancer are actively ongoing. In a phase II study evaluating pembrolizumab and RT in metastatic TNBC patients, 2 out of 5 evaluable patients had a response outside of the irradiated field. Although assessing distant response is not one the endpoints of this protocol, which includes women with non-metastatic breast cancer, the study nevertheless provides proof-of-principle for the concept of systemic immune modulation by RT when added to checkpoint inhibition.

Once safety of the pembro-RT regimen has been established, the efficacy of the regimen remains to be tested. Current chemotherapy regimens (GeparSixto) report pathologic complete response

rates of approximately 50% and in the metastatic setting addition of atezolizumab (PD-L1) to nab-paclitaxel (IMpasion130) showed increased PFS in triple negative breast cancer. Based on these two recent observations, the phase II portion of this trial will test the efficacy of adding pembro-RT to neoadjuvant chemotherapy in early-stage breast cancer and determine the pathologic complete response rate in comparison to best available chemotherapy which is the current standard of care.

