#### ***Recruitment Plan***

At the time of the initial surgical consultation at the Saul and Joyce Brandman Breast Center at Cedars-Sinai, medical oncology or radiation oncology consultation at the Samuel Oschin Comprehensive Cancer Institute at Cedars-Sinai, potentially eligible patients will be identified, informed consent forms provided, and initiation of standard of care treatment (breast conserving surgery or neoadjuvant systemic therapy) dates established. Potentially eligible patients will be evaluated by 1) A designated consenting medical oncologist and 2) consenting radiation oncologist for assessment of amenability to preoperative radiation. All available (per the standard of care) imaging (mammogram +/- breast ultrasound +/- breast MRI) as well as clinical breast exam will be reviewed to assess tumor size and determine feasibility of preoperative radiation boost delivery and thus, study participation. Whenever feasible, the RT evaluation will be arranged prior to the testing date for standard of care treatment so that baseline research bloods may be collected after the patient is confirmed eligible and together with the non-study pretreatment bloods. Prior to protocol intervention, consent will take place at the first available appointment with a consenting professional.

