#### Phase II:

The efficacy endpoint will be pathologic complete response rate (pCR) as determined at the time of surgery assuming that the trial continues through both stages. For this cohort, the pCR rate at the time of surgery which is after RT, pembrolizumab and, in most cases, chemotherapy will be determined. A significance of 0.05 will be used to declare statistical significance. Data from 50 evaluable patients achieve 80% power to detect an effect size

of 1.20 using a two-sided paired t-test at the 0.05 level of significance compared to the historical pCR rate for triple negative breast cancer. The effect size is defined as the difference between the mean pCR rate for this trial compared to historical data for triple-negative breast cancer. This is equivalent to an absolute difference of 20% between the mean pCR rate between the two groups assuming a standard deviation (SD) of 15%.

Comparisons of clinical characteristics for this cohort will be conducted using descriptive summary statistics using median and range. Changes in TIL score, immune populations, gene expression, microbiome populations and cytokine expression will be compared between different time points and responder/non-responder groups if sufficient numbers for analysis are available using the paired t-test or Wilcoxon sign test depending on the distribution of the data.

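### The Phase II pCR comparison is framed as pembro-RT added to neoadjuvant chemotherapy, but it pools patients with and without chemotherapy, so the historical benchmark fits only part of the sample

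*Combined protocol and SAP*

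**What the plan says.** - **Question.** Section 1.3.2 says that "the phase II portion of this trial will test the efficacy of adding pembro-RT to neoadjuvant chemotherapy in early-stage breast cancer" and that the trial will "determine the pathologic complete response rate in comparison to best available chemotherapy which is the current standard of care". The same paragraph puts pCR under current chemotherapy at "rates of approximately 50" per cent.
- **Who may enter.** Sections 4.1 and 4.2 hold one set of criteria for the whole trial. Patients must be candidates for breast-conserving therapy (4.1.12). No item requires planned neoadjuvant chemotherapy, in Phase II or otherwise.
- **What follows study treatment.** Study Schema: "Standard of care treatment is defined as breast-conserving surgery or initiation of neoadjuvant systemic chemotherapy". Section 5.0, Standard of Care Therapy: "The decision to proceed to breast-conserving surgery versus neoadjuvant systemic therapy will be at the discretion of the treating physician". Section 3.0, Recruitment Plan, has "initiation of standard of care treatment (breast conserving surgery or neoadjuvant systemic therapy) dates established" at consultation.
- **What is analysed.** Section 9.2.1 opens by including every subject who received a dose. Its Phase II part takes one pCR rate at surgery, which is "after RT, pembrolizumab and, in most cases, chemotherapy will be determined", and the result is "compared to the historical pCR rate for triple negative breast cancer". It gives no figure for that historical rate. Section 2.4 defines pCR at curative-intent surgery, whatever came before it.
- **Formal rule.** Section 9.1, Phase II, is a Simon two-stage design with a 10% null response rate. It stops at 2 or fewer responses in 22 and rejects at 8 or more in 40.

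**The concern.** A patient operated on about three weeks after the second pembrolizumab dose, with no chemotherapy, counts in the same numerator and denominator as one who completed a chemotherapy regimen. The pooled rate then estimates neither pembro-RT alone nor pembro-RT plus chemotherapy. The benchmark that Section 1.3.2 has in mind applies only to the second group. The words about most cases in Section 9.2.1 show that a mixture is expected, yet the plan has no restriction, stratification or separate report to deal with it.

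At stake is how the Phase II efficacy result is read. If pCR is lower without chemotherapy, a real gain in the chemotherapy group can be diluted until it is no longer visible, by an amount set by how often physicians choose surgery first.

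**Working it through.** **1. The plan's own figures.** For the Simon design, P(reject) is the sum over x = 3 to 22 of P(X1 = x) × P(X2 ≥ 8 − x), with X1 ~ Bin(22, p) and X2 ~ Bin(18, p).

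- p = 0.10: 0.0398 (stated 0.04).
- p = 0.25: 0.803 (stated 0.80).

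Both reproduce.

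**2. Pooled pCR.** Let f be the surgery-first share, c the pCR with chemotherapy and q the pCR without. Then pooled pCR = (1 − f)c + fq. The value c = 0.50 comes from Section 1.3.2; c = 0.70 adds the 20-point difference in Section 9.2.1. The values of f (10 to 30%) and q (0 to 20%) are assumptions, because the documents give neither.

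| c | f | q = 0 | q = 0.20 |
|---|---|---|---|
| 0.50 | 0.10 | 0.90×0.50 = 0.45 | 0.45 + 0.02 = 0.47 |
| 0.50 | 0.30 | 0.70×0.50 = 0.35 | 0.35 + 0.06 = 0.41 |
| 0.70 | 0.10 | 0.90×0.70 = 0.63 | 0.63 + 0.02 = 0.65 |
| 0.70 | 0.30 | 0.70×0.70 = 0.49 | 0.49 + 0.06 = 0.55 |

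With no added effect (c = 0.50) the shortfall is 3 to 5 points at f = 10% and 9 to 15 at f = 30%. With a true 20-point gain (c = 0.70) it is 5 to 7 and 15 to 21 points. Only the second pair should be set against the 20-point gain.

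**3. Effect on the Simon rule.** At the pooled rates for c = 0.50, P(reject) is 0.984 at 35%, 0.998 at 41%, and above 0.999 at 45%, 47% and 50%. The mix hardly moves it. The last figure also shows that the rule rejects almost surely when pembro-RT adds nothing to a 50% chemotherapy rate. It therefore cannot answer the question in Section 1.3.2, with or without mixing.

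**4. Effect on a comparison with 50%.** The plan specifies no such test for 40 patients, so this is an illustration. An exact one-sided test at 0.05 rejects at 26 or more of 40 (actual level 0.040).

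- All 40 on chemotherapy, true pCR 70%: power 0.81.
- f = 10%: power 0.47 to 0.57.
- f = 20%: power 0.16 to 0.32.
- f = 30%: power 0.03 to 0.13.

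**5. Same test restricted to patients planned for chemotherapy.**

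- f = 10%: n = 36, reject at 24 or more (level 0.033), power at 70% = P(Bin(36, 0.70) ≥ 24) = 0.74.
- f = 30%: n = 28, reject at 19 or more (level 0.044), power = P(Bin(28, 0.70) ≥ 19) = 0.68.

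This assumes that those planned for chemotherapy receive it. The smaller denominator costs much less power than the dilution.

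**The case against.** Several counter-arguments stand.

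- **The only coherent decision rule is unharmed.** The Simon conclusion barely changes with the mix, and correcting the population does not make that rule a test against chemotherapy. The null and the unstated benchmark are a separate problem.
- **The size is assumed.** Phase II enrols triple-negative patients with tumours of at least 2 cm, Section 3.0 acknowledges the importance of neoadjuvant therapy for them, and Section 9.2.1 expects most to have it. A 30% surgery-first share has no support in the text. At 10% with no added effect, the shortfall is 3 to 5 points, about 1 to 2 patients in 40, against a standard error of √(0.5×0.5/40) = 7.9 points.
- **The direction is assumed.** If pCR is lower without chemotherapy, mixing works against a claim of benefit and does not create a false one.
- **pCR is not a primary objective in Section 2.0.** It is listed as secondary and again as exploratory. Surgery-first patients remain valid for feasibility and TIL change, and they supply surgical tissue.

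A reader might infer that physicians will route patients by response, choosing at Week 7 after seeing the tumour. The documents do not show this. The Recruitment Plan sets dates at consultation, and the Standard of Care Therapy text speaks of patients planned for neoadjuvant therapy. Nothing bars a later change, and Section 1.6 says the optional MRI may help decide on additional therapy. Response-dependent switching is therefore possible, not established. A reader might also infer that every patient behind the historical rate in Section 9.2.1 had chemotherapy. Only Section 1.3.2 points that way; Section 9.2.1 does not describe them.

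None of this removes the mismatch. The historical comparison is the plan's only route to the Section 1.3.2 question, and it is the part that is mixed.

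**Conclusion.** The concern holds for the historical pCR comparison, as a should-fix. The stated question, the eligibility criteria and the pooled analysis do not line up, and this does not depend on any assumed figure. The size does. With 70% pCR under chemotherapy and 0 to 20% without, pooling gives 63 to 65% at a 10% surgery-first share and 49 to 55% at 30%, so from a quarter of the 20-point gain (5 of 20) to all of it could be lost.

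Two stronger conclusions are not supported. The mix does not invalidate the Simon test. Nor must Phase II eligibility be narrowed: that would exclude patients who are valid for both primary objectives. Because the plan can change after study treatment, grouping by treatment actually received could depend on response, so any grouping should rest on a plan recorded beforehand.

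**What to change.** Keep eligibility and the choice of treatment as they are.

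1. In Section 10.3, record the planned standard of care modality (neoadjuvant chemotherapy or direct surgery) at registration, before C1D1.
2. In Section 9.2.1, Phase II, define the population for the comparison with the historical chemotherapy rate as triple-negative patients with neoadjuvant chemotherapy recorded as the plan before C1D1, whatever is later given.
3. Report pCR separately for patients planned for direct surgery, alongside the all-dosed rate.

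The cost is one registration field and two sentences in Section 9.2.1. Treatment is already planned at consultation, so only the modality needs explicit recording. The downside is a smaller denominator for the historical comparison: 36 of 40 if a tenth are planned for direct surgery.

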### **5.3 Method of Assigning Subjects to Treatment Groups**

There is no randomization. Subjects will be assigned to one of two clinically relevant cohorts per their biomarker profile.

### **5.4 Toxicities and Dosing Delays/Dose Modifications**

Adverse events (both non-serious and serious) associated with pembrolizumab exposure may represent an immunologic etiology. These adverse events may occur shortly after the first dose or several months after the last dose of treatment. Therefore, early recognition and initiation of treatment is critical to reduce complications. Based on existing clinical study data, most irAEs were reversible and could be managed with interruptions of pembrolizumab, administration of corticosteroids and/or other supportive care. For suspected irAEs, ensure adequate evaluation to confirm etiology or exclude other causes. Additional procedures or tests such as bronchoscopy, endoscopy, skin biopsy may be included as part of the evaluation. Based on the severity of irAEs, withhold or permanently discontinue pembrolizumab and administer corticosteroids. Dose modification and toxicity management guidelines for irAEs associated with pembrolizumab are provided in Tables 2 and 3.

Pembrolizumab dose modifications will not be allowed. Pembrolizumab must be withheld for drug-related toxicities and severe or life-threatening AEs as per Table 2 and 3 below. To avoid delay in standard of care treatment, study treatment should be discontinued if toxicities preclude administration of the second dose pembrolizumab as planned. See Pembrolizumab Program Events of Clinical Interest Guidance Document for supportive care guidelines, including use of corticosteroids to treat immune related AEs.

Any patient who receives treatment on this protocol will be evaluable for toxicity.

Radiotherapy is given in a continuous course. It is not anticipated that a treatment break should be needed, as the development of acute skin-related or other side effects is extremely rare. If a break seems necessary due to the development of CTCAE version 4.0 Grade 4 skin or subcutaneous side effects during treatment, or must be given due to unavoidable medical necessity (i.e., intercurrent illness), the situation should be discussed with the treating radiation oncologist. In the event that a patient must miss a scheduled treatment for non-toxicity related reasons (i.e.: weather, sickness, family emergencies, etc) the treatment visit will be made up at the end.

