## 2.4 Endpoints

- **Primary Efficacy Endpoint: Feasibility**

Feasibility will be defined by the number of patients who do not necessitate a delay in standard of care treatment. Since the combination of pembrolizumab and RT has not been tested in the preoperative setting in patients with potentially curative disease, it is necessary to establish whether such preoperative treatment can be safely given without delaying curative-intent treatment.

- **Co-Primary Efficacy Endpoint: Change in TILs**

An increase in TILs is an indicator of immune system engagement. A lead in with pembrolizumab alone followed by the combination of pembrolizumab with RT will allow for serial assessment of TILs. This will establish the contribution of RT to the immune response generated by pembrolizumab.

- **Safety Evaluations**

Immune related adverse events that result from checkpoint blockade can occur weeks after the drugs are administered. Therefore, adverse events will be recorded up to 15 weeks after administration of pembrolizumab and radiation therapy and graded according to CTCAE, Version 4.03. Immune related adverse events will also be documented for up to 1-year post treatment. When considering if an adverse event is immune related, a general principle is that differential diagnoses should be diligently evaluated according to standard medical practice. Non-inflammatory etiologies should be considered.

- **iDFS**

iDFS will be defined as the time from completion of surgery to the first occurrence of the following events: invasive ipsilateral, local, regional, or distant recurrence, or death due to breast cancer.

- **pCR**

pCR will be defined as the absence of invasive disease in the breast and lymph nodes at the time of curative-intent surgery.

---

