### 3.0 STUDY DESIGN

#### ***Study Design***

This is a prospective, single-institution, Phase Ib/II study of the preoperative combination of pembrolizumab (pembro) and radiation therapy (RT) in patients with operable breast cancer (TNBC). The two cohorts will consist of 50 TNBC and 10 HR+ women each. Enrollment will start with the Phase Ib TNBC safety cohort. The trial will be conducted in a Bayesian design, wherein safety as assessed by lack of delay in standard of care treatment will be assessed after 3, 6, and 10 patients have initiated standard of care treatment. If at least 80% of the first 10 subjects in the TNBC cohort proceed with standard of care therapy without delay, the combination will be deemed safe in the cohort, and enrollment in the HR+ cohort, as well as continued enrollment in the TNBC cohort (40 subjects), will occur at that time.

Each cohort will be evaluated for delay in curative-intent standard of care treatment every time 3 patients complete study therapy and undergo standard of care treatment. At each of those timepoints, if the posterior probability that a patient experiences a delay in standard of care treatment exceeds 20%, the cohort will stop enrollment. In Bayesian statistics, the posterior probability of a random event or an uncertain proposition is the conditional probability that is assigned after the relevant evidence or background is taken into account. This design will assure that a cohort does not continue enrollment if early delays in standard of care treatment are seen. Enrollment will be carried out continuously and will not be stopped in order to evaluate the posterior probability of a delay. However, the number of patients undergoing assessment for a possible delay simultaneously will not exceed four in each of the 2 cohorts.

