#### ***Study Intervention***

Patients will receive pembrolizumab Q3W for 2 doses. The second dose will be given in conjunction with an RT boost, consisting of 8 Gy for 3 fractions. We estimate that approximately 10% of patients who are planned to undergo breast-conserving therapy may undergo mastectomy for reasons including positive margins and patient choice. It is anticipated that receipt of a boost dose, which is directed to a small portion (<30%) of the total breast volume, will not preclude the ability to undergo mastectomy.

Approximately 3 weeks after the second dose of pembrolizumab, patients will initiate standard of care curative-intent treatment, consisting of breast surgery or neoadjuvant systemic treatment. Patients will have a pre-planned date for initiation of standard of care treatment scheduled approximately 8 weeks (+/- 5 days) after study initiation. **Research study appointments/interventions will not interfere with the pre-planned, standard of care treatment arrangements.**

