## **9.0 STATISTICAL CONSIDERATIONS**

### **9.1 Sample Size**

#### **Phase Ib:**

It is imperative that any experimental pre-operative therapeutic innovation not undermine the timing of curative-intent treatment in localized breast cancer, the primary endpoint for the Phase Ib study is safety/tolerability, as defined by the number of patients who do not necessitate a delay in standard of care treatment (breast surgery or neoadjuvant systemic therapy followed by breast surgery). A small number of patients of TNBC will be included in this cohort to establish safety of the regimen as described below for consideration for further study. Along with safety, assessment of TILs through the course of treatment in this cohort will establish the immunogenicity of this combination. If at least 80% of the first 10 subjects in the TNBC cohort proceed with standard of care therapy without delay, the combination will be deemed safe in the cohort, and enrollment in the HR+ cohort (10 subjects) will occur at that time.

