## 9.2 Data Sets Analyzed

### Data Analyses/Study Endpoints

#### 9.2.1 Efficacy Analysis

The primary analysis will be based on an intention-to-treat approach and will include all subjects who receive a dose of study drug.

Phase Ib:

The primary efficacy endpoint will be feasibility as defined by the number of patients who do not necessitate a delay in standard of care treatment. Let  $P_d$  be the true probability that a patient experiences a delay. The trial will stop if there is statistical evidence that  $P_d$  exceeds 20%. We will use a Bayesian sequential design by checking whether  $P_d$  exceeds this threshold value after 3, 6, 9, ... patients are evaluable for feasibility. The decision rule is to stop the trial if the posterior probability that  $P_d$  exceeds 0.20 is 0.95 or more;  $P(P_d > 0.2 | \text{data}) > 0.95$ . A non-informative prior distribution for  $P_d$  will be used. Table 9.2.1 gives the stopping rules for the design at each look and column 2 gives the maximum number of patients with delay in order for the trial to proceed. Stopping rules will also apply for any patients with clinical progression of disease during study treatment, although this is expected to be uncommon. For example, if 4 or more delays in treatment are observed after enrolling 6 patients, the trial stops. The third column gives the probability of stopping the trial when in fact, the true  $P_d = 0.20$ . This is the equivalent of the Bayesian type I error probability. The target type I error probability was set at 0.05.

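### The Phase Ib go rule counts only standard-of-care delay yet declares the combination safe; a patient whose toxicity blocks dose 2 can count as a success, or be left out, without ever receiving the combination

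*Combined protocol and SAP*

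**What the plan says.** **Endpoint.** Section 2.4 asks "whether such preoperative treatment can be safely given without delaying curative-intent treatment". Section 9.1 gives the same count a wider label: "the primary endpoint for the Phase Ib study is safety/tolerability, as defined by the number of patients who do not necessitate a delay".

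**Go rule.** Sections 3.0 and 9.1 require at least 80% of the first 10 TNBC subjects to start SOC on time. Section 9.1 states the result: if they "proceed with standard of care therapy without delay, the combination will be deemed safe in the cohort". Under Section 3.0, "enrollment in the HR+ cohort, as well as continued enrollment in the TNBC cohort (40 subjects), will occur at that time".

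**Stopping rule.** Section 9.2.1 and Table 9.2.1 count SOC delays. Section 9.2.1 adds clinical progression as a further event, but not a stop for toxicity.

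**Toxicity before dose 2.** Section 5.4: "To avoid delay in standard of care treatment, study treatment should be discontinued if toxicities preclude administration of the second dose pembrolizumab as planned". Section 3.0, Study Intervention, links radiation to that dose: "The second dose will be given in conjunction with an RT boost".

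**Who is counted.** Section 9.2.1 says the primary analysis "will include all subjects who receive a dose of study drug". Section 3.0 runs the looks "every time 3 patients complete study therapy and undergo standard of care treatment". Section 9.2.1 also refers to patients evaluable for feasibility without defining the term. Section 5.8 lets the PI decide whether to replace patients who do not complete the intervention.

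**The concern.** Section 5.4 acts to prevent the only event that the go decision counts. That is sound care for the patient, but it means the count cannot show how often toxicity ended study treatment before the combination was given. Such a patient may be a success, a failure (if SOC also slips), or absent from the count, depending on her SOC date and on which section is followed. The text never counts the toxicity stop itself.

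What is at stake is the conclusion. A delay count can show that the strategy does not hold up curative treatment. It cannot by itself show that the combination is safe if some of the counted patients never received it, or if they were taken out of the count. That conclusion opens the 40-patient Phase II TNBC part and the HR+ cohort.

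**Working it through.** **Step 1. Reproduce the plan's figures.** Inputs from Table 9.2.1: looks at 3, 6, 9 and 10 patients, with at most 2, 3, 4 and 4 delays to continue. Exact binomial enumeration at a true delay probability of 0.20 gives stopping probabilities of 0.0080, 0.0131, 0.0101 and 0.0113 at the four looks, 0.0424 in total (the table states 0.042). At 0.10 the total is 0.0031 (Table 9.2.2 states 0.003). The tabulated rule is computed correctly; it describes delays only.

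**Step 2. A case that needs no rate.** Three of 10 patients stop for toxicity before dose 2, and all 10 start SOC on time. The go rule scores 10/10 = 100%. The share who received the combination is 7/10 = 70%.

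**Step 3. How much the go probability could be affected.** Let q be the share stopped for toxicity before dose 2 and d the SOC-delay rate among the others. The documents give neither, so both are assumptions. Go means at least 8 successes in 10, so P(go) = P(Bin(10, s) ≥ 8), with s depending on how stopped patients are treated:

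- A, as written, stopped patients on time for SOC: s = 1 − (1 − q)d
- B, stopped patients left out and replaced: s = 1 − d
- C, as written, half of the stopped patients late for SOC: s = 1 − (1 − q)d − 0.5q
- D, for comparison, a toxicity stop counted as a failure: s = (1 − q)(1 − d)

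Worked example, q = 5% and d = 5%: A has s = 1 − 0.95 × 0.05 = 0.9525, P(go) = 0.990; D has s = 0.95 × 0.95 = 0.9025, P(go) = 0.934.

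| d | q | A | B | C | D |
|---|---|---|---|---|---|
| 5% | 2% | 0.989 | 0.988 | 0.982 | 0.973 |
| 5% | 5% | 0.990 | 0.988 | 0.969 | 0.934 |
| 5% | 10% | 0.991 | 0.988 | 0.938 | 0.833 |
| 10% | 10% | 0.946 | 0.930 | 0.846 | 0.708 |
| 10% | 20% | 0.960 | 0.930 | 0.737 | 0.438 |
| 10% | 30% | 0.972 | 0.930 | 0.617 | 0.221 |

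Under A the go probability rises slightly with q, because each stopped patient is on time with certainty. If every stopped patient were late for SOC, the rule as written would equal D and there would be no gap.

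**Step 4. How often would Step 2 occur?** Under A, the probability of a go with three or more toxicity stops is the sum over t = 3 to 10 of P(Bin(10, q) = t) × P(Bin(10 − t, d) ≤ 2). With d = 10% it is 0.011 at q = 5%, 0.068 at 10%, 0.315 at 20% and 0.606 at 30%.

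**Step 5. Does Table 9.2.1 react?** Under A the delay probability is (1 − q)d. With d = 10% and q = 10%, 20% and 30% it is 0.09, 0.08 and 0.07, and the stopping probability is 0.0021, 0.0013 and 0.0008, against 0.0031 at q = 0. The interim rule does not detect this kind of toxicity.

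**The case against.** **The endpoint is deliberate.** Sections 2.1, 2.4, 3.0 and 9.1 all ask whether curative treatment is delayed, and Section 3.0 gives the reason. A patient who stops after dose 1 and starts SOC on time has met that endpoint. This stands. The delay-only count is legitimate; the safety conclusion drawn from it is what goes too far.

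**Toxicity may delay SOC anyway.** Table 2 calls for corticosteroids for most events that withhold pembrolizumab, with a taper of at least 4 weeks. Dose 2 is due at week 4 and SOC at about week 7 to 8. Some stopped patients would therefore be late and already count as failures. This also stands: a reader might infer that a toxicity stop can never be a failure, and the text does not support that. Column C shows the existing rule responding.

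**High stop rates have no support.** These stops would mostly follow a single pembrolizumab dose, and Section 1.5 reports no dose-limiting toxicity for the single agent (in advanced solid tumours, so indirect). A reader might infer from the lower rows of the table that the go rule is likely to pass an intolerable regimen. The documents give no rate from which to say so.

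**Dropping her is a weak reading.** Section 9.2.1 includes all dosed subjects, the go rule uses the first 10, and Section 5.8 does not say that a replaced patient leaves the feasibility count. Fair, but the wording of Section 3.0 and the undefined evaluable set leave the other reading open.

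**Toxicity is watched elsewhere.** It is a secondary objective, related SAEs reach the data and safety monitoring committee within 24 hours (Section 7.6.2), and the research monitor can stop the protocol (Section 10.5.2). This is real protection, but it sets no numerical criterion for the go decision, and the Section 9.2.2 analysis is descriptive.

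**Conclusion.** The point holds in a limited form. The go rule measures SOC delay, and its conclusion should say no more than that. A patient who could not receive the combination because of toxicity counts as a success when SOC is on time and as a failure only when it is late; the texts on who is counted conflict. These findings rest on the wording and need no assumed rate.

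The numerical effect depends on assumptions. With d = 5% it is small at stop rates of 2% to 5%: 0.989 against 0.973, and 0.990 against 0.934. It becomes large only at assumed rates of 10% or more, and shrinks as more stopped patients also miss the SOC date.

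It is tempting to conclude that the plan must use a composite of delay and toxicity stops. The documents do not require this. The 80% bar was set for delay alone, and applying it to a composite would lower P(go) from 0.946 to 0.708 at q = d = 10%, where the composite failure rate is 1 − 0.9 × 0.9 = 19%, still within the bar.

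**What to change.** 1. **Fix the denominator.** In Section 9.2.1, define evaluable for feasibility as having received at least one pembrolizumab dose. In Section 3.0, base the interim looks and the first 10 on that set. In Section 5.8, state that patients who received dose 1 and stopped for toxicity stay in the first 10, and that replacements count only for the TIL analysis.
2. **Match the conclusion to the endpoint.** In Sections 3.0 and 9.1, replace the statement that the combination is deemed safe with one that it does not delay standard of care. Beside the go decision, report how many patients stopped for toxicity before completing both pembrolizumab doses and the three radiation fractions. The data and safety monitoring committee should review that number before Phase II and the HR+ cohort open.

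**Option for the sponsor.** Toxicity stops could be counted as failures in the go rule, but the 80% bar would then need to be reconsidered. At q = 10% and d = 5%, for example, P(go) would be 0.833 instead of 0.991.

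**Cost.** Text changes only, using dosing, radiation, reason-for-stopping and SOC-date records that the trial already keeps. No extra patients or procedures are needed. The price is a narrower go conclusion and one more reported count.
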